Prospective 12-week randomized controlled trial (RCT) of remotely- delivered Customized Adherence Enhancement for poorly adherent individuals with schizophrenia (CAE-S) vs Enhanced Treatment as Usual (eTAU)

NCT number: NCT06061952

Document Date: 12/2/2024

Objectives

This project aims to evaluate the feasibility, acceptability and preliminary efficacy of remotely delivered CAE among patients with schizophrenia (CAE-S). The project will be operationalized in 3 specific aims.

Aim 1: To determine the feasibility and acceptability of administering CAE-S via videoconferencing to patients with schizophrenia. Based on this team's previous work in developing and delivering CAE to individuals with SMI who are poorly adherent with prescribed oral antipsychotic medication¹⁰ and the team's previous work in remotely-delivered engagement and adherence promotion approaches¹⁵, we expect that patients with schizophrenia will be able to receive CAE-S via a telehealth platform and find it highly acceptable.

H1: We expect that CAE-S participants will attend an average of at least 4 CAE sessions.

H2: We expect that at least 75% of participants will agree or strongly agree that the intervention was useful.

Aim 2: To test the pragmatic, clinical effects of CAE-S vs. Enhanced Treatment as Usual (eTAU) on schizophrenia symptoms as measured by the Positive and Negative Syndrome Scale (PANSS) in a randomized control trial (RCT) of 36 poorly adherent patient with schizophrenia.

H3: We expect that patients randomized to CAE-S will have greater improvement from baseline to 12 weeks on PANSS improvement vs. individuals randomized to eTAU.

Aim 3: To explore the effects of CAE-S in improving self-reported medication adherence as measured by the Tablets Routine Questionnaire (TRQ) and validated by electronic pill monitoring (eCAP). We expect that individuals who have improved symptoms of schizophrenia will also have psychotropic medication adherence (TRQ) improvements and improvements in other secondary health outcome measures that are relevant to people with schizophrenia at 12 weeks compared to those randomized to eTAU.

Background

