| 2. | Medical condition or illness, which in the opinion of the research psychiatrist, would interfere with the patient's ability to participate in the trial. |
| 3. | Physical dependence on substances (alcohol or illicit drugs) likely to lead to withdrawal reaction during the course of the study in the clinical opinion of the treated research psychiatrist. |
| 4. | Immediate risk of harm to self or others. |
| 5. | Female who is currently pregnant or breastfeeding. |

Study Design

The project will be implemented as a prospective 12-week RCT of CAE-S vs. enhanced treatment as usual (eTAU) in 36 poorly adherent individuals with schizophrenia. Patients with schizophrenia will be randomly assigned to receive either CAE-S or eTAU following the baseline assessment. The primary feasibility outcomes will be attendance and patient satisfaction (Aim 1) and change from baseline to 12 weeks in schizophrenia symptoms as measured by the Positive and Negative Symptom Scale (PANSS) (Aim 2). An exploratory evaluation (Aim 3) will examine the posited mechanistic underpinnings of the CAE-S intervention by assessing change from screening to 12 weeks in psychotropic medication adherence as measured by the Tablets Routine Questionnaire (TRQ) and validated by eCAP (objective bottle openings). Secondary measures will include the Clinical Global Impression (CGI), functional status, quality of life and attitudes towards medication. Findings will be summarized in at least one manuscript submitted for peer-reviewed publication, paving the way for a larger-scale trial, and will help inform clinicians on care approaches which may optimize antipsychotic medication response in their patients with schizophrenia.

Customized Adherence Enhancement (CAE) Intervention: CAE is an adjunctive (to standard medication treatment) behavioral intervention delivered virtually (real-time one on one video-conferencing) in 6 individual sessions. Because the CAE manual does not target any specific oral antipsychotic medication or group of antipsychotic medications, (it is unbranded) positive

findings from the proposed trial will enhance potential usability across a broad variety of oral antipsychotic medications.

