Enhanced Treatment as Usual (eTAU): Individuals in eTAU will receive an eCAP for their foundational antipsychotic medication and continue to receive care, including prescribed antipsychotic medication with their current non-study providers. Medication adherence behavior typically transiently improves during early phases of focused monitoring (Hawthorne effect), but this wanes over time¹⁶ with expected regression to behaviors existing prior to study enrollment unless otherwise reinforced with an approach like CAE. To optimize control intervention rigor, the eTAU participants will view a pre-taped series of videos (based on NAMI or DBSA general wellness guidelines) 1:1 with a therapist who has similar credentials and competency as the CAE mental health clinician during 6 one-on-one sessions lasting at least approximately 30 minutes. The therapist will view the videos with the participant and field questions the patient may have. This controls for attentional effects, an important consideration in behavioral clinical trials. As an additional consideration to optimize rigor, while study staff are not blinded to intervention assignment, outcomes assessments are collected by non-interventionist research staff, and outcomes data analysts are blinded to the nature of intervention assignment.

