Concomitant medications: This project will not involve the administration of any study drug. CAE is intended to be an adjunct to any standard medication treatment for patients with schizophrenia, and, to increase potential for scale-up and generalizability, CAE can be administered during any phase of medication treatment, including when treatment first begins, during any medication cross-tapers or in the case of polypharmacy treatment. All patients will be receiving treatment with an FDA-approved oral antipsychotic medication, a first-line treatment for schizophrenia as prescribed by their non-study prescribing clinicians. An essential component of CAE is to empower patients and encourage them to communicate with their prescribing clinician when they encounter common roadblocks to staying on track with medications such as side effects or problems with remembering to take the dosing regimen. Participants will also remain on any concomitant medications prescribed by their non-study clinician. The study team will assess medication treatments (drug categories, dosage) and adherence with antipsychotic drugs and all other maintenance treatment with psychotropic medications (TRQ for all prescribed psychotropic treatments, eCAP assessment of foundational antipsychotic drug and directly-observed pill counts done via videoconference) at each research assessment study visit.

Study Procedures

Outcome measures:

Study Measures: As part of the initial clinical evaluation, information will be collected on participant previous illness history including duration of psychiatric illness, previous hospitalizations, previous suicide attempts, medication treatment history (including history of previous treatment-related adverse events), previous history of legal problems and incarcerations and cumulative medical burden as evaluated by the self-reported Charlson Index.

Primary Outcomes:

For Aim 1, primary outcomes for feasibility and acceptability will be assessed via CAE-S attendance (number of sessions attended out of all scheduled sessions) and self-reported patient satisfaction with CAE-S respectively.

For Aim 2, primary outcomes will be schizophrenia symptoms using a standardized, validated measure.

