Attendance and Patient Satisfaction: Attendance will be evaluated as the number of attended CAE sessions (out of a total possible attendance of 6 sessions). This will be a simple count of ranging from 0 (no attended session) to 6 (attended all sessions). In previous work, using CAE to promote oral antipsychotic medication adherence among seriously mentally ill individuals who were poorly adherent, average attendance was 76% with in-person sessions¹⁰. While we believe that attendance will be greater for remotely-delivered vs. in-person, we conservatively estimate that the average attendance with CAE-S will be at least 4 sessions.

Treatment satisfaction will be assessed using a series of self-report items measured on a 5-point Likert Scale from strongly disagree to strongly agree regarding different aspects of the intervention (e.g. the length of sessions, # of sessions, content covered, etc.). This method has been used successfully by our team in multiple treatment outcome studies.⁷⁻¹² In previous work using CAE to promote oral antipsychotic medication adherence among poorly adherent individuals with serious mental illness, 90% felt that the benefit of the intervention exceeded the burden, most (90%) felt that CAE was “about right” in the number of sessions and timing, and all strongly agreed or agreed that CAE addressed all important issues specific to their situation.¹⁰

Schizophrenia Symptoms: Symptoms of schizophrenia disorder will be assessed using the Positive and Negative Syndrome Scale (PANSS) developed by SR Kay et al¹⁷. The PANSS is very widely in research settings. Alpha-coefficient analysis has indicated high internal reliability and homogeneity among PANSS items, with coefficients ranging from 0.73 to 0.83 (p <.001) for each of the scales. The split-half reliability of the General Psychopathology Scale was demonstrated to be 0.80 (p <.001). The authors have also demonstrated the discriminant and convergent validity of the PANSS dimensional assessment in relation to independent clinical, genealogical, psychometric, and historical measures.

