Alcohol and Substance Use: The Alcohol, Smoking and Substance Involvement Screening Test (ASSIST) is a widely used and validated 8-item measure of alcohol and drug use (World Health Organization ASSIST Working Group, 2002).³³

Quality of Life (QoL): The Short Form Health Survey (SF-12) will be used to assess health related quality of life.³⁴ This 12-item self-report Health-related Quality of Life measure has an index for mental health and an index for physical health and has been validated in individuals with serious mental illness.³⁵

[figure not shown]
Schedule of Events

| | Screen | Baseline (~1 week after screen) | Weeks 2-8 | 12 weeks |
|---|--------|------------------------------------|-----------|----------|
| Screening, Informed consent | X | | | |
| Inclusion/Exclusion | X | | | |
| Demographics | X | | | |
| Diagnostic Interview (MINI) | X | | | |
| Medical burden (Charlson) | X | | | |
| Randomization | | X | | |
| eCAP administration and training | X | | | |
| Primary Outcome: Schizophrenia Symptoms - PANSS | | X | | X |
| Secondary outcomes: Adherence Behavior: TRQ, directly-observed pill counts and eCAP* | X | X | | X |
| Secondary outcomes: | | X | | X |

| | | | |
|---------------------------------------|--|--|----------|
| Adherence Attitudes: DAI, PROMIS | | | |
| Global Psychopathology: CGI | | | |
| Social Functioning: Strauss-Carpenter | | | |
| Alcohol/Substance Use: ASSIST | | | |
| Quality of Life: SF-12 | | | |
| Health Resource Use | | | |
| CAE sessions/attendance | | | X |
| ETAU sessions/attendance | | | |
| Participant satisfaction | | | X |

*eCAP data collection will start at baseline following distribution at screen

Figure 1: Study Design

Data Analysis Plan

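### Nothing in the plan withholds allocation from the staff who rate the week-12 PANSS, the only efficacy primary outcome

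*Combined protocol and SAP*

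**What the plan says.** Blinding is covered in one sentence, at the end of the eTAU paragraph in Study Design: "while study staff are not blinded to intervention assignment, outcomes assessments are collected by non-interventionist research staff, and outcomes data analysts are blinded". No other section adds to it.

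Other parts of the plan bear on the point:

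- **Outcome.** The Schedule of Events lists "Primary Outcome: Schizophrenia Symptoms - PANSS" at baseline and 12 weeks. The Data Analysis Plan names PANSS change as the primary outcome and bases its power statement on it. The other primary outcomes, attendance and satisfaction, concern feasibility and acceptability.
- **Timing.** Under Study Design, participants are "randomly assigned to receive either CAE-S or eTAU following the baseline assessment".
- **Control arm.** eTAU has six one-to-one sessions with a therapist of similar standing. The plan says of this: "This controls for attentional effects, an important consideration in behavioral clinical trials".
- **Satisfaction.** Primary Outcomes defines acceptability as "self-reported patient satisfaction with CAE-S respectively". The section on attendance and satisfaction adds: "Treatment satisfaction will be assessed using a series of self-report items". Neither says who administers the items or whether eTAU participants receive them.
- **Purpose.** Objectives states the aim as to "evaluate the feasibility, acceptability and preliminary efficacy of remotely delivered CAE", and Study Design describes the findings as "paving the way for a larger-scale trial".

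**The concern.** Not delivering the intervention is different from not knowing who received it. The plan requires the first of its assessors and is silent on the second, while stating that study staff in general are unblinded. A rater who knows the arm and expects CAE-S to work may score the week-12 PANSS more favourably in that arm. The baseline score is protected because randomization comes later, so the whole of any such shift enters the change score. Blinded analysts cannot take it out, and matching the arms on contact does not address rater expectation.

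In a pilot the main cost is an effect estimate that is too favourable and is carried into the design of the larger trial. A raised false-positive rate is secondary. Attendance is a count and satisfaction is self-reported, so neither depends on a symptom rater.

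The plan shows one possible route to unblinding. Staff who administer items about satisfaction with CAE-S could learn the arm from doing so, and nothing says that these are different people from the PANSS raters.

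**Working it through.** **1. The plan's own power figure.** The Data Analysis Plan gives a decrease of 6.7 with SD 7.1, one-sided alpha 0.05, 28 evaluable participants and 77% power. Attrition is 36 × 0.23 = 8.3, leaving about 28, or 14 per arm. The noncentral t, with n multiplied by the Wilcoxon relative efficiency of 0.955 and a standardized difference of 6.7/7.1 = 0.944, gives 76.7%. The stated figure reproduces. Blinding the raters changes none of its inputs.

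**2. Inputs for the illustration.** True effect 0; 14 per arm; common SD 7.1 (the SD of the earlier observed decrease); one-sided 0.05. The one-sided level is stated only for the power calculation; the analysis text gives no sidedness. The rating shift b, applied in the CAE-S arm only, is purely assumed.

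**3. Formula.** SE of the difference = 7.1 × √(2/14) = 2.68. The false-positive rate is P(T > 1.706), where T is noncentral t with 26 df and noncentrality b/2.68. For b = 2 the noncentrality is 0.745. The exact Wilcoxon rank-sum rates come from simulation, 100,000 trials per cell. With b = 0 the rates are 5.0% (t) and 4.7% (Wilcoxon).

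**4. All CAE-S ratings shifted.**

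| Shift b (points) | b / 6.7 | t | Wilcoxon |
|---|---|---|---|
| 1 | 15% | 10.0% | 9.5% |
| 2 | 30% | 17.9% | 16.8% |
| 3 | 45% | 28.9% | 26.8% |

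**5. Only a fraction of CAE-S ratings exposed, b = 2.** The mean bias is the fraction times 2 points. Rates are simulated for both tests.

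| Fraction exposed | Mean bias (points) | t | Wilcoxon |
|---|---|---|---|
| 90% | 1.8 | 16.0% | 14.8% |
| 75% | 1.5 | 13.5% | 12.6% |
| 50% | 1.0 | 10.0% | 9.3% |
| 25% | 0.5 | 7.2% | 6.6% |

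**6. Sensitivity, b = 2, all exposed (t / Wilcoxon).** SD 10: 12.9% / 11.9%. SD 14: 10.1% / 9.4%. Two-sided 0.05 test, favourable direction only (2.5% under the null): 10.7% / 10.2%. With no attrition (18 per arm, one-sided, SD 7.1): 20.7% / 19.7%.

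**7. Precision for comparison.** At 14 per arm the two-sided 95% interval for the difference has half-width 2.056 × 2.68 = 5.5 points. A 2-point bias is 2/2.68 = 0.75 of a standard error.

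**The case against.** The strongest reply is that this is silence, not a demonstrated fault. The sentence contrasts unblinded study staff with non-interventionist assessors and is offered as a measure of rigor, so it can be read as setting the raters apart. They may already be shielded in practice, in which case only a clarification is needed and nothing is gained in bias. That stands as a limit: what is certain is that rater blinding is not stated, not that ratings are biased. It does not remove the point, because a team following the text as written could let raters know the arm.

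The sizes are also open to challenge. The shift has no source in the documents. Neither current exposure nor exposure after the change is known. Going from 50% to 25% exposed would lower the rate only from about 10% to about 7%. The figures therefore show how the design responds to bias and do not estimate a gain. A 2-point bias is also smaller than the sampling error of so small a trial. That is true, but bias is systematic and sampling error is not.

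The satisfaction route is conjectural: the items are self-report, and their example topics could suit either arm. This too stands, and the route is put forward only as a possibility. Finally, a statement of blinding by itself changes nothing. The information has to be withheld in practice, and even then participants may disclose their sessions.

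**Conclusion.** The concern holds, as a recommended improvement. The plan separates raters from therapists and blinds the analysts, but it does not keep allocation from the people who score the week-12 PANSS. Four features limit the exposure: non-interventionist raters, blinded analysts, randomization after baseline, and a control arm with the same number of individual sessions, so that contact alone does not give the arm away. None of them stops knowledge of the arm, if a rater has it, from moving the score.

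Confidence is high that the safeguard is absent from the text. The size of any bias cannot be determined from the documents. Under the stated assumptions, a 1- to 3-point shift in every CAE-S rating would give a false-positive rate of about 9% to 29% in place of 5%, and would inflate the estimate by 15% to 45% of the planning difference. Both fall as fewer ratings are exposed or, for the false-positive rate, as the SD rises.

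**What to change.** Amend the blinding sentence in the eTAU paragraph so that study staff described as unblinded no longer include the outcome raters. State that the existing non-interventionist raters of the week-12 PANSS, and of other rater-scored scales such as the CGI, are blinded to arm, and that allocation and session or attendance records are withheld from them. Have the satisfaction items self-completed or handled by other existing staff. Optionally, record each unblinding event so that its extent can be reported.

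This needs no new visit, test or participant, and power is unchanged. The cost is the possible reassignment of tasks that reveal the arm: randomizing, scheduling sessions, logging attendance and collecting satisfaction. The documents do not say who does these, so the cost cannot be stated exactly; it is larger if one person does them all and also rates. The benefit is partial, and small if most participants reveal which sessions they had.

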patient's pattern of pill-taking behavior. Although many patients with schizophrenia take multiple antipsychotic medications, we will monitor the antipsychotic dosed most often (index drug). If more than one drug is dosed at the same frequency, the antipsychotic most recently added to the regimen will be the index drug. As-needed or "prn" drugs will not be monitored. In previous work by this study team, the correlation between a single "index" drug and all drugs was 0.95 providing support for measuring one medication as proxy for medication adherence.²³ The method of choosing an index drug also limits participant burden. To ensure that the data collected represent pill-taking behavior as accurately as possible, patients will be instructed to (1) dispense doses of their monitored medication only from the eCAP equipped bottle, (2) remove only one dose at a time, and (3) remove a dose only at the time that they plan to swallow the medication. Adherence is defined as the % of pills missed, and a ratio of number of doses missed to number prescribed will provide a percentage, with a higher value indicating poorer adherence. While just assessing adherence behavior may temporarily increase adherence (e.g., the Hawthorne effect), it is expected that any potential impact on adherence behavior will wane over the 3 month follow-up. A large recent clinical trial demonstrated limited long-term adherence advantage for passive medication aids (e.g., 7-day pill organizer, pill cap displaying time since last dose), a category into which eCAP would fall.²⁴ Experience with eCAP conducted by this team yielded substantially less missing data using the eCAP than the MEMS. Adding an extra financial incentive for bringing in the eCAP (\$10 per visit) optimizes use of automated pill-monitoring. Notably, in a recent pilot study, 31/38 participants (81.6%) brought their eCAP to all 3 study visits over a 6-month period.²⁵ To optimize generalizability, individuals who use medisets or pill-minders to manage multiple medications will not be excluded from the study. We will follow the same procedure that we did for a recent study which was very effective. Only one medication will be tracked via eCAP. All other medications can remain in the pill-minder or other medication tracking device. The medication is placed in the eCAP by the research assistant (RA) when setting up the device if in person or the RA will instruct the participant to do so during their video-conferencing meeting. Participants will be trained on the use of eCAP and will have the opportunity to practice opening the cap before it is activated.

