Statistical Analysis: Our study proposes to assess the primary outcome of change from baseline to week 12 on the PANSS. Expected magnitude of change is informed by results of 2 previous studies using CAE in schizophrenia by these PIs ([name] 2013, [name] 2017). We will conduct descriptive analysis of baseline variables (i.e., age, gender, ethnicity, and level of education). The PANSS total will be a sum of global symptoms of schizophrenia. First, we will compare the changes in PANSS from baseline to 12 weeks, respectively, for the CAE-S and eTAU groups using a non-parametric Wilcoxon rank-sum test to determine whether the subgroup medians differ. Should baseline-covariates differ between subgroups, we will conduct the appropriate multivariable linear regression for normalized outcome measures, to account for residual confounding. Analysis of the secondary outcomes will be conducted in a similar manner. An intent-to-treat analysis will be conducted. We will assess the missing at random assumption for the mixed models for missing data due to dropout or missed assessments.

We project a sample size of 36 subjects, randomized in equal numbers (CAE=18, eTAU= 18). In our previous study using CAE and long-acting injectable antipsychotic medication in homeless individuals with schizophrenia, 10 (33%) out of 30 subjects dropped out after 24

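### The eCAP is handed out about a week before randomisation, but the plan does not provide for a pre-randomisation eCAP value, which costs precision and part of the TRQ validation

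*Combined protocol and SAP*

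**What the plan says.** The points below are from the combined protocol and SAP.

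- **Schedule of Events.** eCAP hand-out and training are marked at Screen. Baseline follows about one week later, and Randomization is marked at Baseline. The row "Secondary outcomes: Adherence Behavior: TRQ, directly-observed pill counts and eCAP" is marked at Screen, Baseline and 12 weeks. Its footnote reads: "eCAP data collection will start at baseline following distribution at screen".
- **Study Design.** Patients "will be randomly assigned to receive either CAE-S or eTAU following the baseline assessment". Aim 3 looks at TRQ change from screening to 12 weeks, with eCAP as the validating measure.
- **Concomitant medications.** TRQ, eCAP and directly observed pill counts are to be assessed at every research assessment visit.
- **eCaps.** Adherence is doses missed divided by doses prescribed. No time window is given. Participants "will have the opportunity to practice opening the cap before it is activated", but no activation date is stated.
- **Data Analysis Plan.** PANSS change from baseline to week 12 is compared by Wilcoxon rank-sum test. Then: "Analysis of the secondary outcomes will be conducted in a similar manner". In the power paragraph, eCAP again serves to validate TRQ.

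**The concern.** The footnote separates two events: the cap is distributed at screen, and data collection begins at baseline. On its ordinary meaning, the week in which a trained participant already holds the device yields no data. Because randomisation takes place at the baseline visit, no eCAP value would then precede allocation.

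Two things follow. First, eCAP is listed as a secondary outcome, and secondary outcomes are to be handled like PANSS change, so an eCAP change is implied that could not be calculated. Nor could the arm comparison be adjusted for starting eCAP adherence. Second, eCAP is meant to validate a TRQ change that begins at screen, but it would have data only for the later end of that change.

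The earlier end is where a check is most useful. TRQ is self-reported, and missing 20% or more on it is an entry criterion, so the screening value is a selected one. An electronic value that played no part in selection would help show how much of the later TRQ change is real.

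**Working it through.** **1. Timeline, under each reading of the footnote**

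| | Recording starts at baseline | First read-out is at baseline |
|---|---|---|
| eCAP at screen | none | none |
| Screen-to-baseline week | not recorded | recorded, but no scoring rule |
| Pre-randomisation eCAP value | none | possible, undefined |
| eCAP change to week 12 | cannot be formed | can be formed once windows are set |
| Post-baseline eCAP compared between arms | valid | valid |

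Under both readings there is no eCAP value at screen, where the TRQ change starts, and the eCAP windows are undefined.

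**2. Do any stated figures depend on eCAP?**

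Inputs from the Data Analysis Plan: 36 randomised 1:1; attrition 23% (36 × 0.23 = 8.28, taken as 8), leaving 28, or 14 per arm; one-sided alpha 0.05; PANSS 6.7 (SD 7.1); TRQ 37 points (SD 36.9), or 37 − 5 = 32 if eTAU changes by 5. A two-sample t calculation with the Wilcoxon efficiency factor 3/π gives:

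| | Stated | Recomputed |
|---|---|---|
| PANSS | 77% | 76.6% |
| TRQ, no eTAU change | 81% | 80.9% |
| TRQ, 5% eTAU change | 71% | 70.4% |

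The plan's figures reproduce. None uses eCAP, so none is affected.

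**3. Chance imbalance in starting adherence**

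With 18 per arm, the standardised baseline difference has standard error √(2/18) = 0.33 SD. A gap of at least that size in either direction arises by chance in about 32% of trials.

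**4. What a pre-randomisation value could add**

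The documents give no correlation r between baseline and week-12 eCAP, so r is assumed. Relative to comparing week-12 values alone (variance 1), covariate adjustment has variance 1 − r² and a change score has 2(1 − r).

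| Assumed r | Covariate | Change score | Equivalent completers, 28/(1 − r²) |
|---|---|---|---|
| 0.2 | 0.96 | 1.6 | 29.2 |
| 0.3 | 0.91 | 1.4 | 30.8 |
| 0.5 | 0.75 | 1.0 | 37.3 |

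The cut is 9% at r = 0.3 and 25% at r = 0.5. Below r = 0.5 a change score is worse than ignoring baseline, so the value belongs in the model as a covariate.

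Estimating the slope from 28 people also has a price, a factor of about 1 + 1/(28 − 4) = 1.042 on the variance. The net factors are 0.96 × 1.042 = 1.00, 0.91 × 1.042 = 0.95 and 0.75 × 1.042 = 0.78. At r = 0.2 the precision gain vanishes.

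**5. How noisy is one week?**

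Assume once-daily dosing (7 doses) and independent misses. The standard error of a participant's percent missed is √(p(1 − p)/7): 0.15 at p = 0.2 and 0.19 at p = 0.5. Noise of that size lowers r, so the lower part of the range is more plausible.

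**The case against.** The strongest reply is that the footnote merely explains why the Screen mark does not apply to eCAP: the cap has just been handed out and holds nothing to read. The first data would then be collected at baseline and cover the preceding week. The Baseline mark, the assessment at every research visit and the randomisation after the baseline assessment all fit this. It cannot be ruled out. It is not stated either. The row is shared with TRQ and pill counts, so its marks do not settle what happens to eCAP, and no section says that the week is recorded, read or scored.

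Other parts of the reply stand:

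- No section names an eCAP change analysis. It is implied by a general sentence and a schedule label, while the named role of eCAP is to validate TRQ.
- Randomisation makes a comparison of post-baseline eCAP valid without any baseline value.
- TRQ and directly observed pill counts, the latter not self-reported, are both marked before randomisation and could serve as proxy covariates. The protocol gives pill counts no scoring rule or window, though.
- The protocol expects adherence to rise briefly when monitoring begins, so the first week may be unrepresentative.
- The equivalent-completer figures assume that all 28 have usable eCAP data. In the pilot cited under eCaps, 31 of 38 (81.6%) brought the cap to every visit. At that rate it would be 28 × 0.816, or about 23.

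A reader might infer that the trial loses its only objective adherence measure, or that the adherence comparison cannot be made. The points above show that the documents support neither.

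**Conclusion.** The point holds as a gap that should be closed at low cost. On the literal reading there is no pre-randomisation eCAP value. On the alternative reading one may exist, but it is neither defined nor assigned a use. Either way, the plan does not say how eCAP validates a TRQ change that starts at screen.

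The effect is confined to an exploratory aim and a secondary measure. PANSS, attendance, satisfaction and every stated power figure are untouched. The precision at stake is a variance cut of 9% at r = 0.3 and 25% at r = 0.5 (about 5% and 22% net of estimating the slope with 28 completers), and it is probably near the low end. These figures rest on an assumed r, a linear adjustment and complete eCAP data. Percent missed is bounded and may be skewed, so they are approximate. The validation benefit does not depend on r in this way, and it is the steadier reason for the change.

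**What to change.** 1. Reword the footnote so that the cap is activated and records from distribution at screen, once practice openings are finished, and is read at the baseline visit before randomisation.
2. Define baseline eCAP as percent of prescribed doses missed from activation to the baseline visit, and state the window for week-12 eCAP.
3. Prespecify the arm comparison of post-baseline eCAP with baseline eCAP as a covariate, not as a change score. The plan currently brings in regression only if baseline covariates differ, so this needs its own sentence. A rank-based version would suit skewed data.
4. Set the recorded week beside the past-week TRQ taken at baseline, which covers nearly the same days, and use the pair as the pre-randomisation anchor for validation. State how this bears on a TRQ change that starts at screen.

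If a baseline read-out was always intended, the same wording settles the ambiguity. The cost is one extra read-out at an existing visit, with no new device, visit or staff. The first week may show monitoring reactivity, but that precedes allocation and so cannot bias the comparison between arms.
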